9.2.1 DFCI/BWH Testing of Pre-Post Treatment Tumor Tissue

An example of the DFCI prescreening results that may be generated prior to trial entry is described below. In addition, all Cohort 1 on surgery samples will be tested post-treatment tissue using these same assays for comparison to pre-treatment tissue. DFCI FFPE tumor tissue from the participant's surgery prior to enrolling onto the study or Cohort 1 post-treatment tissue will be genotyped with the clinically validated OncoPanel targeted exome sequencing for 300 cancer causing genes and whole genome OncoCopy Agilent array comparative genomic hybridization at 1M probe resolution, and the results correlated with outcome. Both assays are performed in the CLIA-certified laboratory at the Dana-Farber/Brigham and Women's Cancer Center, Center for Advanced Molecular Diagnostics (CAMD).

9.2.1.1 OncoCopy Whole Genome Array CGH (DFCI/BWH)

Tissue requirements for aCGH are 10 x 5 µm standard formalin-fixed paraffin embedded (FFPE) tumor sections or 5 x 0.5 mm tissue cores containing at least 50% tumor nuclei and less than 10% necrosis. At least 1.3 u µg tumor DNA (nanodrop quantification) is required. As previously described, aCGH is performed using DNA fragmentation simulation methods (FSM) with Agilent SurePrint G3 1x1M arrays (Craig et al., 2012). Whole genome data are generated and analyzed using proprietary cytogenomics software. Copy number aberrations (CNAs) are curated to prioritize genetic events most likely to have diagnostic, prognostic and/or therapeutic significance in brain tumors in order to generate a genotyping list of at least 40 different genomic imbalances. The time required from tissue submission to data reporting averages two weeks or less. A distinct advantage of this assay is that whole genome data may be reanalyzed at later time points or in exploratory arms of the study without additional cost. In addition, the use of a dedicated and robust copy number assay whose performance is well characterized allows for inclusion of more reproducible results in future studies.

9.2.2 OncoPanel Targeted Exome Sequencing (DFCI/BWH)

DNA will be isolated from 5-10 5 µm FFPE slides or 3 x 0.6 mm tissue cores, frozen tissue or genomic DNA from a CLIA lab containing at least 50% tumor nuclei using routine extraction methods previously described (Wagle et al., 2012). At least 200ng of genomic dsDNA is required (PicoGreen quantification). Somatic mutations in tumor DNA will be detected using the high-throughput targeted deep sequencing OncoPanel in the DF/BWCC CLIA-certified laboratory at the Brigham and Women's Hospital (Center for Advanced Molecular Diagnostics-CAMD, Molecular Pathology [name], Director). Briefly, massively parallel sequencing libraries (Illumina) that contain barcoded universal primers will be generated using genomic DNA from FFPE tumor material to be used in solution-phase hybrid capture with biotinylated RNA baits. Sequencing data is analyzed for single nucleotide sequence variants, small insertions/deletions, and DNA copy-number alterations in exons from 275 actionable cancer genes including oncogenes and tumor suppressors.

9.2.3 Immunohistochemistry Correlates for Cohort 1 Patients

Tumor from all patients will be evaluated by IHC for PD (including the levels of pRB1, CC3, Ki67, and other markers of abemaciclib), tumor microenvironment, as well as immunologic changes in pre or pre-post treatment pairs. These studies will require a total of 17 IHC unstained plus slides cut at 5um thickness (Cohort 1 and 2, archived and study surgery). Ten slides should be sent to [name] at DFCI and 7 slides (on Superfrost Plus glass slides) should be sent to [name] at UCLA. This is for correlation only and is not utilized for trial entry/screening.

9.3 Special Studies

Cell Line Sample:

Primary glioblastoma patient derived cell lines (PDCLs) derived from glioblastoma participants have been shown to retain key genetic and expression characteristics of the parent tumor and offer a potentially advantageous exploratory mechanism for biologic analysis of response in individual participant tumors as well as potential diagnostic predictor of participant response to drug. Primary glioblastoma cell lines develop successfully from roughly half of all attempts at culturing. Attempted culturing of PDCLs is expected for all Cohort I surgeries. In addition, for participants who are also enrolled in the Ivy Stage 0 tissue banking protocol, cells lines established at new diagnosis may be available. As such we will seek to study and compare responses to abemaciclib in any participant cell lines which are derived by participating sites from newly diagnosed or treated participant specimens at recurrence. Cell lines will be studied for the dynamic response to abemaciclib in vitro as read out by similar IHC, Western, and pharmacodynamic measures described for tissue samples above (e.g., pRb reduction, KI-67 measurement of proliferation index). These studies will be coordinated or performed by the laboratory of [name] at DFCI.

To achieve a cell line, an additional sample (200mg size of green pea or larger) should be sent fresh to the local hospital research lab for establishment of a participant primary cell line (serum free, neurosphere methods) by the site's standard procedures. If the local site does not have capability or would prefer the fresh tissue can be submitted in RMPI media to [name] lab for culture instead of the local site. This should be shipped at 4 degrees on wet ice. All cell lines derived from the study participants will be shared with the site of referral. For sites that create cell lines locally the central site (DFCI, [name]) will request frozen aliquot of live cells in DMSO – if available – at a later date (may be \sim 6 months after surgery); but this is not a mandated study submission.

10. STUDY CALENDAR

Table 10 describes required procedures. All procedures may increase in frequency if clinically indicated or oriented following a toxicity/adverse event.

Table 10.1 Required Activity Calendar for Cohort 1 only

Fuenciastica	_ , a		urgery	During	Post-	30-Day Post
Examination	Screening	D1 ^b	D8 ^c	Surgery	Surgery ^e	Drug ^f
Informed consent ^g	Х					
Background Information	Х					
Inclusion/Exclusion Criteria h	Х					
Serum Pregnancy Test ⁱ	Х	Х				
Vital Signs ^j	Х					
Neuro & Physical Exam	X					
KPS ^k	Х					Х
Con-Med & Adverse Event		XX				
Assessments I				X		
12-lead ECG	X					
Imaging – MRI ^m	Х					
Hematology ⁿ	Х	Х	Х			
Serum Chemistry °	Х	Х	Х			
Coagulation (PT/INR, PT, PTT)	X					
Submission of Archival Tissue p	Х					
Blood for Immunophenotyping ^q		Х		Х		
Plasma PK Collection ^r		Х	Х	Х		
Tumor Resection ^s				Х		
Abemaciclib Administration ^t		Every 12 hours including none none				

- a. To be performed within 14 days of registration unless specified otherwise.
- b. Pre-surgery Day 1 assessments to be performed within 3 days prior to drug day 1 unless specified otherwise.
- c. Pre-surgery Day 8 assessments to be performed within +/- 1 day.
- d. Surgery to occur after participant is on daily drug for 10-14 days. Abemaciclib is to be taken on the morning of/before the surgery 1-3 hours prior to surgery and tumor removal. Since participants in cohort 1 are undergoing PK testing, accurately regarding the time of study drug administration on day of surgery and recording the time of tumor removal are especially required. Procedures to be documented during surgery, and samples to be collected, are detailed in section 9.
- e. Post-surgery period is the time following surgery. No protocol specific assessments are required for this period; sites may obtain assessments as clinically indicated.
- f. A contact/visit for review of concomitant medications, adverse events, and KPS (no neurologic exam required at 30-day FU time point) is to be performed at 30 days + 7 days after the last study drug is given. This may be performed via documented phone conversation with a study nurse or clinician. All participants will be followed until resolution or stabilization of any serious adverse events occurring during treatment or starting within 30 days of last study drug

- g. Per DF/HCC multi-center policy, must be obtained by MD attending. Informed Consent may be performed up to 28 days prior to registration Per DF/HCC multi-center policy, must be obtained by MD attending. Informed Consent may be performed up to 28 days prior to registration.
- h. Please see section 3. Genomic profiling data from previously performed sequencing and/or copy number array data to verify status of CDKN2A/B/C and RB1 must be available prior to registration.
- i. Serum pregnancy test only for women of child bearing potential (as defined in Section 3.1.20). Serum pregnancy test within 7 days prior to Day 1 drug for registration purposes and repeated within 72 hours prior to Day 1 drug if original screening pregnancy test is not within 72 hours of Day 1 drug.
- j. Vital signs: Weight, heart rate, blood pressure, respiration rate, temp. Height required only at baseline (any height within 1 year of registration is acceptable).
- k. Karnofsky Performance Status (KPS)
- I. Adverse events experienced by participants will be collected and reported from initiation of study medication, throughout the study, and within 30 days of the last dose of study medication. Participants who experience an ongoing adverse event related to a study procedure and/or study medication beyond 30 days will continue to be contacted by a member of the study team until the event is resolved, stabilized, or determined to be irreversible by the participating investigator. Concomitant medications and reason for administration should be documented in the case history from date of consent up to the 30-Day Post Drug Visit.
- m. Imaging: gadolinium-enhanced contrast and non-contrast MRI. CT alternative, if MRI contraindicated. When feasible at a site, appendix G MRI Acquisition Protocol should be adhered to Imaging: gadolinium-enhanced contrast and non-contrast MRI. CT alternative, if MRI contraindicated. When feasible at a site, appendix G MRI Acquisition Protocol should be adhered to and the same imaging technique should be used in a participant throughout the trial. Screening baseline scan within 14 days prior to registration.
- n. Hematology erythrocytes (RBC), hemoglobin, hematocrit, platelets, total WBC plus differential (neutrophils, lymphocytes, monocytes, eosinophils, basophils)Hematology erythrocytes (RBC), hemoglobin, hematocrit, platelets, total WBC plus differential (neutrophils, lymphocytes, monocytes, eosinophils, basophils).
- o. Biochemistry albumin, alkaline phosphatase (ALP), bicarbonate (HCO₃), BUN, calcium, chloride, creatinine, glucose, magnesium, phosphorous, potassium, SGOT (AST), SGPT (ALT), sodium, total protein, total bilirubin, amylase and lipase, LDH and uric acid. If total bilirubin is greater than the upper limit of normal, direct and indirect bilirubin should be performed.
 - Coagulation assays of PT/INR, PT, PTT required at screening only.
- p. Archival tumor tissue per eligibility point 3.1.11 must be submitted to the DFCI Coordinating Center within 60 days of registration.
- q. Required at pre surgery C1D1 (pre-dose) and prior to the morning dose on the day of surgery.
- r. Required at pre surgery C1D1 (pre-dose), pre-surgery Day 8 (pre-dose), and day of surgery at the time of tumor resection for Cohort 1 participants.
- s. See section 9 for details on tumor tissue requirements. On-study surgery tissue should be submitted within 60 days of date of surgery.
- t. Please see protocol section 8.1.8 for abemaciclib administration instructions

Table 10.2 Required Activity Calendar for Cohort 2 only

Examination	Screening ^a	Су	cle 1	Subsequent Cycles	End of	30-day post	Long Term
	oci cerming	D1 ^b	D15 ^C	D1 ^d	тх ^е	drug ^f Fo	Follow Up ^g
Informed Consent ^h	Х						
Background Information	Х						
Inclusion/Exclusion Criteria ⁱ	Х						
Serum Pregnancy Test ^j	Х	Х		Х			
Vital Signs ^k	Х	Х	Х	Х	Х		
Neuro & Physical Exam	Х	Х	Х	Х	Х		
KPS	Х	Х	Х	Х	Х	Х	
Con-Med & Adverse Event				X			
Assessments ^m				A			
12-lead ECG	χn			χn			
Imaging – MRI ^O	χр	χр		Xo	Х		
Response Assessment ^q				Х	Х		
Hematology ^r	Х	Х	х	Х	х		
Serum Chemistry ^S	Х	Х	Х	Х	Х		
Coagulation (PT/INR, PT, PTT)	Х						
Submission of Archival Tissue	χ ^t						χw
Plasma PK Collection ^U		Х		Х			
Abemaciclib Administration ^V		Every 12 hours		Every 12 hours			
Follow-Up Info							Х

- a. To be performed within 14 days of registration unless specified otherwise.
- b. To be performed within 3 days prior to drug day 1 unless specified otherwise.
- c. Cycle 1, Day 15 visit has a +/- 2 days window.
- d. Within 3 days prior to day 1 drug, except imaging which is within 7 days prior to day 1 drug. Results of all assessments (aside from correlative studies) must be reviewed prior to taking drug for respective cycle.
- e. End of treatment assessments to be performed within +/- 7 days of last study drug or within +/- 7 days of decision to end treatment. All participants will be followed until resolution or stabilization of any serious adverse events occurring during treatment or starting within 30 days of last study drug.
- f. A contact/visit for review of concomitant medications, adverse events, and KPS (no neurologic exam required at 30-day FU time point) is to be performed at 30 days +7 days after the last study drug is given. This may be performed via documented phone conversation with a study nurse or clinician. All participants will be followed until resolution or stabilization of any serious adverse events occurring during treatment or starting within 30 days of last study drug.
- g. Participants will be followed via medical record review until death for post-treatment therapies, progression information, and survival. Updates to the CRFs are to be made roughly every three months (+/- 1 month). Each site will be responsible for collecting information on their participants regarding all post-treatment therapies, start and stop dates of those therapies, the reason for stopping those therapies, and the date of death.
- h. Per DF/HCC multi-center policy, must be obtained by MD attending. Informed Consent may be performed up to 28 days prior to registration.

- i. Please see section 3. Genomic profiling data from previously performed sequencing and/or copy number array data to verify status of CDKN2A/B/C and RB1 must be available prior to registration.
- j. Serum pregnancy test only for women of child bearing potential (as defined in Section 3.1.20). Serum pregnancy test within 7 days prior to Day 1 drug for registration purposes and repeated within 72 hours prior to Day 1 drug if original screening pregnancy test is not within 72 hours of Day 1 drug.
- k. Vital signs: Weight, heart rate, blood pressure, respiration rate, temp. Height required only at baseline (any height within 1 year of registration is acceptable).
- I. Karnofsky Performance Status (KPS)
- m. Adverse events experienced by participants will be collected and reported from initiation of study medication, throughout the study, and within 30 days of the last dose of study medication. Participants who experience an ongoing adverse event related to a study procedure and/or study medication beyond 30 days will continue to be contacted by a member of the study team until the event is resolved, stabilized, or determined to be irreversible by the participating investigator. Concomitant medications and reason for administration should be documented in the case history from date of consent up to the 30-Day Post Drug Visit.
- n. EKG at screening and C2D1 only.
- o. Imaging: gadolinium-enhanced contrast and non-contrast MRI. CT alternative, if MRI contraindicated. When feasible at a site, appendix G MRI Acquisition Protocol should be adhered to and the same imaging technique should be used in a participant throughout the trial. Imaging to be done at all odd cycles (C3D1, C5D1, etc.).
- p. Within 14 days prior to registration (screening baseline scan). For the scan prior to treatment cycle 1 day 1, if steroids are added or increased between the date of the scan and the start of treatment, new baseline imaging is required.
- q. Response assessment using RANO criteria, at time of imaging and as indicated clinically.
- r. Hematology erythrocytes (RBC), hemoglobin, hematocrit, platelets, total WBC plus differential (neutrophils, lymphocytes, monocytes, eosinophils, basophils).
- s. Biochemistry albumin, alkaline phosphatase (ALP), bicarbonate (HCO₃), BUN, calcium, chloride, creatinine, glucose, magnesium, phosphorous, potassium, SGOT (AST), SGPT (ALT), sodium, total protein, total bilirubin, amylase and lipase, LDH and uric acid. If total bilirubin is greater than the upper limit of normal, direct and indirect bilirubin should be performed.
- t. Archival tumor tissue per eligibility point 3.1.11 must be submitted to the DFCI Coordinating Center within 60 days of registration Archival tumor tissue per eligibility point 3.1.11 must be submitted to the DFCI Coordinating Center within 60 days of registration.
- u. Required at C1D1 (pre-dose), C2D1, C3D1 and C4D1 for Cohort 2 participants. If a participant comes off study treatment prior to C4D1 then an end of treatment PK sample should be drawn. See section 9 for details on PK timing and processing requirements.
- v. Please see protocol section 8.1.8 for abemaciclib administration instructions.
- w. Tissue from subsequent surgery or post-mortem exam: In the event that the participant undergoes any subsequent surgery for tumor resection, if possible, tumor tissue will be acquired to evaluate potential mechanisms of resistance to therapy with abemaciclib. [name] should be consulted for specifications prior to surgery when possible.

166 A

11. MEASUREMENT OF EFFECT

This trial will utilize the criteria recently proposed by the Response Assessment in Neuro-Oncology (RANO) working group (Wen et al., 2010).

Radiologic assessment will be determined by the Response Assessment in Neuro-Oncology Working Group (RANO) Criteria using bidirectional tumor measurements with some modifications. In addition to imaging characteristics, these criteria include consideration of neurological function and corticosteroid use (Wen et al., 2010). The RANO Criteria is outlined in detail in this section.

Magnetic resonance imaging (MRI) is the most readily available and reproducible method of disease assessment and is required for this study. The largest and most representative lesions should be measured either on axial, coronal or sagittal slices, and chosen to be followed for response evaluation.

The recommended sequences are outlined in detail in Appendix G and should conform as closely as possible to the consensus recommendations for a standardized Brain Tumor Imaging Protocol in clinical trials.

11.1 Antitumor Effect – Definitions

Evaluable for toxicity. All participants who receive at least one dose of study treatment will be evaluable for toxicity from the time of their first treatment.

Evaluable for objective response. Only those participants who have measurable disease present at baseline (cycle 1, day 1 scan) and have received at least one dose of therapy will be considered evaluable for response. These participants will have their response classified according to the definitions stated below. (Note: Participants who exhibit objective disease progression or die prior to the end of cycle 1 will also be considered evaluable.)

Measurable disease. Bidimensionally, contrast-enhancing, measurable lesions with clearly defined margins by CT or MRI scan, with a minimal diameter of 1 cm, and visible on 2 axial slices which are at least 5 mm apart with 0 mm skip. Measurement of tumor around a cyst or surgical cavity, if necessary, requires a minimum thickness of 3 mm. If there are too many measurable lesions to measure at each evaluation, the investigator must choose the largest two to be followed before a participant is entered on study. The remaining lesions will be considered non-measureable for the purpose of objective response determination. Unless progression is observed, objective response can only be determined when all measurable and non-measurable lesions are assessed.

Non-measurable evaluable disease. Unidimensionally measurable lesions, masses with margins not clearly defined, lesions with maximal diameter < 1cm.

11.2 Response/Progression Categories

Complete response (CR). All of the following criteria must be met:

- a) Complete disappearance of all enhancing measurable and non-measurable disease sustained for at least 4 weeks. In the absence of a confirming scan 4 weeks later, this scan will be considered only stable disease.
- b) No new lesions.
- c) All measurable and non-measurable lesions must be assessed using the same techniques as baseline.
- d) Participants must be on no steroids or on physiologic replacement doses only.
- e) Stable or improved non-enhancing (T2/FLAIR) lesions
- f) Stable or improved clinically, for clinical signs and symptoms present at baseline and recorded to be disease related

Participants with non-measurable disease cannot have a complete response. The best response possible is stable disease.

Partial response (PR). All of the following criteria must be met:

- a) Greater than or equal to 50% decrease compared to baseline in the sum of products of perpendicular diameters of all measurable enhancing lesions sustained for at least 4 weeks. In the absence of a confirming scan 4 weeks later, this scan will be considered only stable disease.
- b) No progression of non-measurable disease.
- c) No new lesions.
- d) All measurable and non-measurable lesions must be assessed using the same techniques as baseline.
- e) The steroid dose at the time of the scan evaluation should be no greater than the dose at time of baseline scan.
- f) Stable or improved non-enhancing (T2/FLAIR) lesions on same or lower dose of corticosteroids compared to baseline scan.
- g) Stable or improved, for clinical signs and symptoms present at baseline and recorded to be disease related clinically.

Participants with non-measurable disease cannot have a partial response. The best response possible is stable disease.

Progressive disease (PD). The following criterion must be met:

a) > 25% increase in sum of the products of perpendicular diameters of enhancing lesions (over best response or baseline if no decrease) on stable or increasing doses of corticosteroids

and/or one or more of the of the following:

b) Significant increase in T2/FLAIR non-enhancing lesion on stable or increasing doses of corticosteroids steroids compared to baseline scan or best response following initiation of therapy, not due to co-morbid events (radiation therapy, demyelination, ischemic injury, infection, seizures, post-operative changes, or other treatment effects).

- c) Any new lesion
- d) Clear clinical deterioration not attributable to other causes apart from the tumor (e.g. seizures, medication side effects, complications of therapy, cerebrovascular events, infection, etc.). The definition of clinical deterioration is left to the discretion of the investigator but it is recommended that a decline in the Karnofsky Performance Score (KPS) from 100 or 90 to 70 or less, a decline in KPS of at least 20 from 80 or less, or a decline in KPS from any baseline to 50 or less, for at least 7 days, be considered neurologic deterioration, unless attributable to co-morbid events or changes in corticosteroid dose.
- e) Failure to return for evaluation due to death or deteriorating condition

Stable disease (SD). All of the following criteria must be met:

- a) Does not qualify for CR, PR, or progression.
- b) All measurable and non-measurable sites must be assessed using the same techniques as baseline.
- c) Stable non-enhancing (T2/FLAIR) lesions on same or lower dose of corticosteroids compared to baseline scan. In the event that the corticosteroid dose has been increased, the last scan considered to show stable disease will be the scan obtained when the corticosteroid dose was equivalent to the baseline dose.
- d) Stable clinically.

Unknown response status. Progressive disease has not been documented and one or more measurable or non-measurable lesions have not been assessed.

These RANO Response Criteria are also summarized in the following table:

Table 10.2: Summary of the RANO Response Criteria

	CR	PR	SD	PD#
T1-Gd +	None	≥50% decrease	<50% decrease- <25% increase	≥25% increase*
T2/FLAIR	Stable or decrease	Stable or decrease	Stable or decrease	Increase*
New Lesion	None	None	None	Present*
Corticosteroids	None	Stable or decrease	Stable or decrease	NA
Clinical Status	Stable or increase	Stable or increase	Stable or increase	Decrease*
Requirement for Response	All	All	All	Any*

CR=complete response; PR=partial response; SD=stable disease; PD=progressive disease

NA: Increase in corticosteroids alone will not be taken into account in determining progression in the absence of persistent clinical deterioration

^{#:} Progression occurs when any of the criteria with * is present

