As the study continued, the nonsurgical cohort (Cohort 2) completed accrual while the surgical cohort (Cohort 1) remained open. Outcomes data were reviewed in the nonsurgical cohort (Cohort 2) demonstrating limited benefit from abemaciclib monotherapy with a PFS6 rate of 9.37% [95% CI, 2.4%, 22.27%], median PFS 55 days [95% CI, 49, 56], and median OS 384 days [95% CI, 228, 488]. Nonetheless, a surgical cohort still provides valuable information to understanding why abemaciclib has limited activity in recurrent GBM patients and whether it helps enhance the antitumor immune response (Goel et al., 2017). Therefore, the study was amended further to convert the remaining slots in the surgical cohort (Cohort 1) into a Phase 0 study. The study design remains the same (pretreatment with abemaciclib followed by surgery with correlative studies) except that participants will come off study treatment after surgery and pursue standard cancer treatments as per the treating physician's discretion. The purpose of this phase 0 study is not to treat the tumor but to determine tumor tissue PK and PD. This phase 0 study does not replace routine cancer treatment.

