- 16. Participants having undergone recent resection or open biopsy or stereotactic biopsy of recurrent or progressive tumor will be eligible for Cohort 2 as long as the following conditions apply:
 - o They have recovered from the effects of surgery.
 - Residual disease following resection of recurrent tumor is not mandated for eligibility. To best assess the extent of residual disease post-operatively, an MRI

or CT scan should ideally have been performed no later than 96 hours following surgery, or at least 28 days post-operatively, but scans performed outside of this window are considered acceptable if no alternative is available. In either case, the baseline/screening MRI must be performed within 14 days prior to registration. If the participant is taking corticosteroids, the dose must be stable or decreasing for at least 5 days prior to the scan. If steroids are added or the steroid dose is increased between the date of the screening MRI or CT scan and the start of treatment, a new baseline MRI or CT is required.

Clinical labs – performed within 14 days prior to registration

17. Hematology:

- Absolute neutrophil count (ANC) \geq 1.5 x K/ μ L
- Platelet count $\geq 100 \text{ x K/}\mu\text{L}$
- Hemoglobin $\ge 8.0 \text{ g/dL}$

18. Biochemistry:

- o Total serum calcium (corrected for serum albumin as needed) or ionized calcium within institution's normal range.
- o Magnesium within institution's normal range.
- o AST (SGOT) and ALT (SGPT) \leq 3.0 x institution's ULN
- Serum bilirubin \leq 1.5 x institution's ULN. Patients with Gilbert's syndrome with a total bilirubin \leq 2.0 times ULN and direct bilirubin within normal limits are permitted.
- o Serum creatinine ≤ 1.5 x institution's ULN or calculated 24-hour creatinine clearance ≥ 50 mL/min
- Serum amylase ≤ 1.5 x institution's ULN
- Serum lipase ≤ 1.5 x institution's ULN

19. Coagulation studies:

- o INR < 2.0
- o PTT ≤ institution's ULN, unless receiving therapeutic low molecular weight heparin or oral factor Xa inhibitors.

Pregnancy and Reproduction

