11.4 Evaluation of Best Response

The best overall response is the best response recorded from the start of the treatment until disease progression (taking as reference for progressive disease the smallest measurements recorded since the treatment started). If a response recorded at one scheduled MRI does not persist at the next regular scheduled MRI, the response will still be recorded based on the prior scan, but will be designated as a non-sustained response. If the response is sustained, i.e. still present on the subsequent MRI, it will be recorded as a sustained response, lasting until the time of tumor progression. Participants without measurable disease may only achieve SD or PD as their best "response."

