13.4 Analysis of Secondary and Exploratory Endpoints

Response rate will be the proportion of participants with measurable disease who experience complete or partial radiographic response determined by the RANO Criteria (Wen et al., 2010). Progression free survival, PFS6, and overall survival will be calculated using standard statistical methods. Safety will be summarized using descriptive statistics. Participants in Cohort 2 will not be replaced for any reason. If a subject enrolled in Cohort 1 is found at the time of on-treatment re-resection to have only necrosis and not recurrent disease, then s/he may remain on treatment but should be replaced for evaluation of endpoints.

In Cohort 1 & 2 plasma, and Cohort 1 tumor tissue levels of abemaciclib will be determined by liquid chromatography coupled with tandem mass spectrometry. Descriptive details of steady-state trough plasma levels, CSF and tumor tissue concentrations and tumor tissue to plasma ratios will be provided.

Other pharmacodynamic studies including immunohistochemistry and quantitative IHC analysis will be performed as in Section 9.0. Effects of abemaciclib on tumor cell proliferation and tumor cell death will be measured using immunohistochemistry for pRB1, Ki-67 and Cleaved Caspase 3. In general the pharmacodynamic and neuro-imaging results will be summarized in a descriptive manner with comparison between pre- and post-treatment assay results when possible.

Beyond the assessment of "success", more detailed analyses of the biological correlate data are exploratory. The statistical analysis will depend on the amount and quality of the data obtained as well as the overall success of the treatment.

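### A response that is never confirmed and is gone at the next scheduled MRI is stable disease under 11.2 but a recorded response under 11.4, and 13.4 does not say which counts in the Cohort 2 response rate

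*Combined protocol and SAP*

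**What the plan says.** Section 11.2 sets a duration requirement for both complete response (CR) and partial response (PR). For PR it asks for at least a 50% decrease "in the sum of products of perpendicular diameters of all measurable enhancing lesions sustained for at least 4 weeks". Under both categories it adds: "In the absence of a confirming scan 4 weeks later, this scan will be considered only stable disease".

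Section 11.4 defines best overall response. Where a response seen at one scheduled MRI has not persisted at the next, it says "the response will still be recorded based on the prior scan, but will be designated as a non-sustained response". If the response is still there at the next MRI, it is labelled sustained.

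Section 13.4 defines the endpoint: "Response rate will be the proportion of participants with measurable disease who experience complete or partial radiographic response determined by the RANO Criteria". It mentions neither confirmation nor the sustained/non-sustained label. On where those criteria are set out, the introduction to Section 11 says: "The RANO Criteria is outlined in detail in this section".

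Table 10.2 (footnote o) schedules Cohort 2 imaging at odd-numbered cycles only, and Section 13.1 gives the same 8-week interval. No confirming scan at 4 weeks is scheduled.

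**The concern.** Radiographic response rate is a Cohort 2 secondary objective (1.3.2) and a listed secondary endpoint (13.2.2.2). For one kind of patient, two stated rules give opposite classifications and the analysis section does not choose between them. The ambiguity works in one direction: counting unconfirmed, lost responses can only raise the rate.

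Timing adds to the problem. Section 2.4 states: "Outcomes data were reviewed in the nonsurgical cohort (Cohort 2) demonstrating limited benefit from abemaciclib monotherapy". A rule chosen now would be chosen after outcomes were seen.

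Sites could also diverge. Central review under 11.6 starts from a site's own determination of CR, PR or PFS6. A site applying 11.2 would not send such a patient as a responder; a site applying 11.4 could. Section 11.6 does not say which rule the central reviewer uses.

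**Working it through.** **1. The two rules applied to the same patients**

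| Course | 11.2 | 11.4 | Conflict? |
|---|---|---|---|
| PR at week 8, no interim scan, still PR at week 16 | PR (sustained at least 4 weeks) | Response, sustained | No |
| PR at week 8, confirmed by an extra scan at least 4 weeks later, gone at week 16 | PR | Response, non-sustained | No |
| PR at week 8, no interim scan, gone at week 16 | Stable disease | Response, non-sustained | **Yes** |

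The conflict is confined to the third row. With scans only every 8 weeks, that is the ordinary form of a lost response; the second row needs an unscheduled scan.

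**2. Does another section settle it?**

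- Section 11.1 says evaluable participants are classified by the definitions that follow it. This leans towards 11.2 but does not exclude 11.4.
- The summary table at the end of 11.2 lists PR as a decrease of at least 50%, with no confirmation requirement.
- Section 13.5 covers only who is evaluable.
- The introduction to Section 11 says RANO is used with some modifications and places the criteria in Section 11, which contains both rules.

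**3. Size**

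The plan gives no target, power or precision for the response rate, so there is no figure of that kind to reproduce. The stated Cohort 2 design figures concern PFS6. For success at 8 or more of 32, the exact binomial gives power 0.918 at 35% (stated 0.92) and probability of rejection 0.904 at 15% (stated 0.90). CR/PR status does not enter that rule.

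For the response rate, one reclassified patient moves the estimate by 1/n. The largest possible n is 32 (13.3). It may be smaller, because the endpoint needs measurable disease and 3.1 (criterion 16) says "Residual disease following resection of recurrent tumor is not mandated for eligibility". The number with measurable disease is not given, so 24 and 20 are assumptions.

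- 1/32 = 3.1 points; 1/24 = 4.2 points; 1/20 = 5.0 points.

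The exact (Clopper-Pearson) 95% limits for x responders of n are the 0.025 quantile of Beta(x, n−x+1) and the 0.975 quantile of Beta(x+1, n−x). For x = 0 the lower limit is 0 and the upper is 1 − 0.025^(1/n); at n = 32 this is 10.9%. As an illustration, suppose there are no confirmed responses and either 0 or 3 disputed ones:

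| n | Rate if disputed patients are not counted | Rate if 3 disputed patients are counted |
|---|---|---|
| 32 | 0% (0 to 10.9%) | 9.4% (2.0 to 25.0%) |
| 24 (assumed) | 0% (0 to 14.2%) | 12.5% (2.7 to 32.4%) |
| 20 (assumed) | 0% (0 to 16.8%) | 15.0% (3.2 to 37.9%) |

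A single disputed patient gives 1/32 = 3.1% (0.1 to 16.2%) or 1/20 = 5.0% (0.1 to 24.9%).

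**4. How many are likely?**

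Two 28-day cycles put C3D1 at day 57, and the scan may be up to 7 days early, so the first on-treatment MRI falls on about days 50 to 57. Section 2.4 reports median PFS of 55 days (95% CI 49 to 56). About half of the 32 had therefore progressed or died by around that scan and could not show a response at it. Few disputed patients are to be expected.

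**The case against.** The strongest reply is that 13.4 already means 11.2. CR and PR are defined only there, and the sentence introducing the summary table calls those categories the RANO criteria. Section 11 also contains a neurological scale and shipping instructions, so being in Section 11 does not make 11.4 part of RANO. On this reading 11.4 only attaches a durability label to responses that already qualify, and an interim scan, though not scheduled, is allowed when clinically indicated.

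This is a reasonable reading and probably the better one, but the text does not require it. Section 11.4 is not limited to confirmed responses. It compares consecutive scheduled MRIs, between which no scan is planned, and it is the section that defines best overall response. An analyst could follow it in good faith.

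A second reply is that 2.4 reports PFS6, PFS and OS but no response rate, so it does not show that response classification was reviewed or is still open. That is correct. It is nevertheless enough that any clarification would now follow a review of Cohort 2 outcomes.

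A third is that the effect may be nil: no disputed patient is known, and the endpoint is descriptive with no threshold. This stands as a limit on the size of the problem. It does not remove the contradiction.

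**Conclusion.** The concern holds. Sections 11.2 and 11.4 classify the same unconfirmed, lost response differently, and 13.4 does not choose. Each such patient changes the Cohort 2 response rate by 3.1 points at the maximum denominator of 32, and by more if fewer have measurable disease. The three-patient illustration and the denominators of 24 and 20 are assumptions, and the true number of disputed patients is probably small. The PFS6 rule of 8 of 32 is untouched. So is treatment, because CR, PR and SD all continue until progression or unacceptable toxicity (5.3). This should be corrected before the response rate is reported, but it does not threaten the primary conclusion.

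**What to change.** Add one rule to 13.4 and refer to it from 11.2 and 11.4, along these lines:

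*The response rate counts CR and PR that meet Section 11.2. Any scan at least 4 weeks later, including the next scheduled 8-week MRI, can confirm. A response with no confirming scan that is gone at the next scheduled MRI is stable disease for best response; the number of such responses is reported separately.*

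Keep the non-sustained label in 11.4 as a description of durability only. Letting the 8-week MRI confirm avoids discarding durable responses merely because no scan fell at 4 weeks.

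Date the clarification and state that it was written after Cohort 2 outcomes were reviewed. Report the rate both ways, with exact 95% intervals and the number with measurable disease, so that the late choice cannot be taken for a selective one.

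The cost is a wording change and one extra line in the response table, with no additional scan or patient. The main rate may be slightly lower than under 11.4, and the rule is still fixed after outcomes were seen, which is why both rates should be shown.
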